10. APPENDICES

Appendix 1 – Adverse Event Definitions

In emergency situations, the investigator should immediately get in touch with the sponsor's pharmacovigilance contact at the telephone number or email address given on the title page of this protocol.

Patients will be evaluable for safety if they have received at least part of 1 plitidepsin infusion/control arm. Adverse events (AEs) will be graded according to the National Cancer Institute-Common Terminology Criteria for Adverse Events (NCI-CTCAE) version 5.0.

[http://ctep.cancer.gov/protocolDevelopment/electronic_applications/docs/CTCAE_v5_Quick_Reference_8.5x11.pdf]

Treatment compliance, i.e., dose delays, dose reductions and reasons for treatment discontinuation, will be monitored throughout the study.

The safety profile of patients will be monitored throughout the treatment and up to 28 days (± 3 days) after the last treatment infusion, or until the date of death, whichever occurs first.

Any treatment-emergent AEs (TEAE; the term TEAE covers any unfavourable or unintended sign, symptom, syndrome, or illness, including laboratory abnormalities that develop or worsens during the period of observation in the clinical study) will be followed until recovery to at least Grade 1 or stabilisation of symptoms or death, whichever occurs first. After treatment discontinuation, patients will be followed until resolution or stabilisation of all toxicities, if any. Patients having any treatment-related Grade ≥ 3 AEs should have relevant tests re-assessed at least every 72 hours until recovery to at least Grade 2.

Adverse Event Definitions

Adverse Event

An AE is any untoward medical occurrence in a patient or clinical investigation patient administered a pharmaceutical product, which does not necessarily have a causal relationship with this treatment.

An AE can therefore be any unfavourable and unintended sign, (e.g., an abnormal laboratory finding), or a disease temporally associated with the use of a medicinal product, whether or not considered related to the medicinal product.

Illnesses with onset during the study or exacerbations of pre-existing illnesses, including but not limited to clinically significant changes in physical examination findings and abnormal objective tests/procedures findings (e.g., X-ray, electrocardiogram) should be recorded. The criteria for determining whether an abnormal objective test finding should be reported as an AE are as follows:

- The test result is associated with clinically significant symptoms, and/or
- The test result leads to a change in the study dosing or discontinuation from the clinical trial, significant additional concomitant drug treatment or other therapy, and/or

- The test result leads to any of the outcomes included in the definition of a serious AE (SAE; see definition below), and/or
- The test result is considered to be clinically relevant by the investigator.

Serious Adverse Event

A SAE is defined as any adverse experience occurring at any dose that:

- results in death (is fatal)
- is life-threatening
- requires or prolongs inpatient hospitalisation
- results in persistent or significant disability or incapacity
- is a congenital anomaly or birth defect, or
- is medically significant.
- any suspected transmission via a medicinal product of an infectious agent.

Medical and scientific judgement should be exercised in deciding whether expedited reporting is appropriate in other situations, such as an important medical event that may not be immediately life-threatening or result in hospitalisation but may jeopardise the patient or may require intervention to prevent one of the outcomes listed in the above definition.

Death

Death is the outcome of an SAE and should not be used as the SAE term itself. The cause of death should be recorded as the SAE term instead. When available, the autopsy report will be provided to the sponsor.

Life-threatening Event

A life-threatening event is defined as any event in which the subject is at risk of death at the time of the event; it does not refer to an event which hypothetically might have caused death if it were more severe.

Hospitalisation/Prolongation of Hospitalisation

Any event requiring hospitalisation (or prolongation of hospitalisation) that occurs or worsens during the course of a patient's participation in a clinical study must be reported as an SAE unless exempted from SAE reporting. Prolongation of hospitalisation is defined as any extension of an inpatient hospitalisation beyond the stay anticipated/required for the initial admission, as determined by the investigator or treating physician.

Hospitalisations that do not meet criteria for SAE reporting are:

- Reasons described in the protocol (e.g., investigational medicinal product [IMP] administration, protocol-required investigations). However, events requiring

hospitalisation or prolongation of hospitalisation as a result of a complication of therapy administration or clinical study procedure will be reported as an SAE.

- Hospitalisation or prolonged hospitalisation for technical, practical or social reasons, in the absence of an AE.
- Pre-planned hospitalisations: Any pre-planned surgery or procedure must be documented in the source documentation. Only if the pre-planned surgery needs to be performed earlier due to a worsening of the condition should this event (worsened condition) be reported as an SAE.

Other situations that MUST NOT be considered as hospitalisations are:

- An emergency visit due to an accident where the patient is treated and discharged.
- When the patient is held 24 hours for observation and is finally not admitted.
- Planned treatments at sites not associated to a hospital and generally considered as minor surgical procedures (i.e., laser eye surgery, arthroscopy, etc.).

Unexpected/Unlisted Adverse Event

An AE is considered unexpected/unlisted when the nature or severity of which is not consistent with the applicable reference safety information (RSI). The sponsor will use as the RSI for the evaluation of listedness/expectedness the RSI of the most updated IB for plitidepsin.

Adverse Reaction

All untoward and unintended response to an IMP related to any dose administered. This definition also covers medication errors and uses outside what is foreseen in the protocol, including overdose, misuse and abuse of the product.

Adverse Events Related to the Study Drug

An AE is considered related to a study drug/IMP if the investigator's and/or the sponsor's assessment of causal relationship to the IMP(s) is "Y (yes)". The investigator will assess the causal relationship of the IMP(s) to the SAE. The sponsor will consider related to the study drug(s)/IMP(s) those events for which the investigator and/or the sponsor assesses the causal relationship with the IMP(s) as "Uk (unknown)" when it cannot rule out a role of the IMP(s) in the event.

Expedited Reporting

The sponsor is responsible for appropriate expedited reporting to the competent authorities, the investigators, and the IEC/IRB according to current legislation.

Assessment of Causal Relationship to the Study Drug

The investigator must provide an assessment of causality for the IMP according to the following criteria:

- Y (yes): there is a reasonable possibility that the IMP(s) caused the AE/SAE.
- N (no): there is NO a reasonable possibility that the IMP(s) caused the AE/SAE and other causes are more probable.
- UK (Unknown): only to be used in special situations where the investigator has insufficient information (i.e., the patient was not seen at his/her centre). If none of the above can be used.

Adverse Event Reporting Procedures

Reporting of Adverse Events

The sponsor will collect all AEs until 28 days (± 3 days) after administration of the last dose of any of the study arms (plitidepsin and control arm) or until the date of death, whichever occurs first. All AEs suspected to be related to the study drug(s)/IMP(s) must be followed-up after the time of therapy discontinuation until the event or its sequelae resolve or stabilise at an acceptable level to the investigator and the sponsor.

All AEs, including medication errors and uses outside what is foreseen in the protocol, must be recorded in English using medical terminology in the source document and the eCRF. Whenever possible, the investigator will record the main diagnosis instead of the signs and symptoms normally included in the diagnoses.

Investigators must assess the severity (Grade) of the event following the NCI-CTCAE version 5.0 and assign a relationship to each study drug(s)/IMP(s); and pursue and obtain information adequate both to determine the outcome and to assess whether it meets the criteria for classification as an SAE requiring immediate notification to the sponsor or its designated representative. The investigator must provide any relevant information as requested by the sponsor in addition to that on the eCRF.

Abnormal laboratory tests occurring during the study must only be recorded in the AE section of the eCRF if the disorder:

- Is associated with clinically significant symptoms, and/or
- Leads to a change in study dosing (omission, delay or reduction) or discontinuation from the study, significant additional concomitant drug treatment or other therapy, and/or
- Leads to any of the outcomes included in the definition of an SAE.

Otherwise, laboratory results should be reported in the corresponding section of the eCRF (e.g., biochemistry, haematology).

The “Adverse event form” will be used only for events that occur after the first drug infusion or any event related to a study procedure within the study period (according to International Conference on Harmonisation [ICH] guidelines); and to report ‘ongoing’ baseline conditions in case of any significant change (improvement or worsening) during the study.

Reporting of Serious Adverse Events

The sponsor will collect all SAEs from the time of signing of the ICF and until 28 days (± 3 days) after administration of the last dose of any of the study arms (plitidepsin and control arm) or until death, whichever occurs first. Beyond this period of time, only those SAEs suspected of being related to the IMPs will be collected. Nonetheless, the sponsor must evaluate any safety information related to the clinical study that is spontaneously reported by an investigator beyond the time frame specified in the protocol.

All SAEs (as defined above) that have occurred after patient registration, regardless of relationship to the study drug(s)/IMP(s), must be reported immediately, and always within 24 hours to the Pharma Mar S.A. Pharmacovigilance Department electronically by completing the applicable eCRF section. Only in situations of electronic system failure or pregnancy exposure during the clinical trial, can SAEs be reported using paper on a “SAE form by fax ([contact]) or email ([contact]). Outside of office hours (Greenwich Meridian Time [GMT]), assistance on SAE reporting can be obtained by calling the Pharmacovigilance Department at [contact]. In case of electronic system failure or pregnancy exposure during the clinical trial, SAEs initially reported by alternative methods (not electronically), must be followed by completed electronic SAE reporting on an eCRF from the investigational staff within 1 working day.

The SAEs occurring during the screening phase (from ICF signature to registration) and after off-study will be reported using a paper “SAE form” that must be forwarded as mentioned above always within 24 hours to the Pharma Mar S.A. Pharmacovigilance Department by fax or email.

All SAEs suspected to be related to the study drug must be followed until the event or its sequelae resolves or stabilises to at least Grade 1, or to an acceptable level according to the investigator and the sponsor or his/her designated representative.

Reporting of Pregnancy Cases Occurring During the Clinical Study

National regulations require that the sponsor collect information on pregnancies occurring during clinical trials, in which exposure to the study drug at any time during pregnancy, via either maternal or paternal exposure, is suspected.

Therefore, pregnancy and suspected pregnancy (including a positive pregnancy test regardless of age or disease state) of a female patient or the female partner of a male patient occurring while the patient is on study drug, or within 31 days of the patient’s discontinuation visit, are considered immediately reportable events.

The investigator will report the following events immediately and always within 24 hours from first knowledge:

- Any occurrence of a pregnancy where any kind of exposure to the study drug is suspected.
- Possible exposure of a pregnant female.

- All reports of elevated/questionable or indeterminate beta human chorionic gonadotropins.

Immediately after detecting a case of suspected pregnancy in a female clinical trial patient, the decision on her continued participation in the clinical trial will be jointly taken by the trial patient, the investigator and the sponsor with the patient's best interest in mind. A decision to continue the pregnancy will require immediate withdrawal from the trial.

Any pregnancy, suspected pregnancy, or positive pregnancy test must be reported to the Pharmacovigilance Department at Pharma Mar immediately by facsimile or email using the pregnancy report form.

The investigator will follow the pregnancy until completion/termination, and must notify the outcome of the pregnancy to the Pharmacovigilance Department at Pharma Mar within 24 hours of first knowledge as a follow-up to the initial pregnancy report.

For any event during the pregnancy which meets a seriousness criterion (including foetal or neonatal death or congenital anomaly), the investigator will also follow the procedures for reporting SAEs (complete and send the SAE form to Pharmacovigilance Department at Pharma Mar by facsimile ([contact]) or by email ([contact]) within 24 hours of the investigator's knowledge of the event).

All neonatal deaths that occur within 30 days of birth should be reported, regardless of causality, as SAEs. In addition, any infant death at any time thereafter that the investigator suspects as related to the in-utero exposure to the study drug should also be reported to the Pharmacovigilance Department at Pharma Mar by facsimile within 24 hours of the investigators' knowledge of the event.

Adverse Events Monitoring

Safety review will be performed at Pharma Mar S.A. once the SAE forms have been received and the eCRFs have been completed by the investigator.

Periodic safety review of clinical data will be performed; however, no formal Data Safety Monitoring Board has been appointed for this trial. The AEs will be monitored by the investigators and by the study team at Pharma Mar S.A. The personnel in charge of this process are defined in the section "Study Contacts" of this protocol. In general, a clinical virologist, together with a member of the Pharma Mar S.A. Pharmacovigilance Department will review the safety data of this trial on an ongoing basis.

- SAEs will be collected, assessed and reported as per the applicable regulations by the Pharmacovigilance Department.
- Nonserious AEs will be checked for accuracy against the eCRF during monitoring visits by the monitor.

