- Patients with SAEs: 22% (10/45) of patients experienced SAEs, including 6 dosed at 1.5 mg, 1 dosed at 2.0 mg, and 3 dosed at 2.5 mg ([Table 2](#)). With the exception of one case of anaphylactic reaction, all these events were related to COVID-19 infection.

- Patients with AEs: No dose-related trends were noted for any reported AEs. Importantly, the safety profile for COVID-19 patients treated with a cumulative dose of up to 7.5 mg plitidepsin (2.5 mg/day x 3) in the APLICOV-PC study was consistent with that established for cancer patients receiving their first cycle of treatment at the equivalent of 8.75 mg/day plitidepsin (5 mg/m² x 1.75 m² average body surface area) on a Days 1 and 15 q4w schedule. The most commonly reported AEs included gastrointestinal disorders of constipation (18% *versus* 19% for COVID-19 and cancer patients, respectively), diarrhoea (18% *versus* 16%), nausea (42% *versus* 44%), and vomiting (18% *versus* 23%); constitutional symptoms of asthenia/fatigue (13% *versus* 62%) and pyrexia (47% *versus* 11%); nervous system disorders of dizziness (7% *versus* 5%) and headache (13% *versus* 7%); and respiratory symptoms of cough (24% *versus* 14%) and dyspnoea (16% *versus* 13%).
- Changes in laboratory parameters: Although 62% of patients showed ≥ 1 grade change in haematology parameters and 84% of patients showed ≥ 1 grade change in chemistry parameters on study, few patients showed >1 grade shift. For haematology parameters, 6 patients had lymphopenia worsen by 2-3 grades and 2 had neutropenia worsen by 2-3 grades. For chemistry parameters, 5 patients had ALT increase by 2-3 grades, 2 had AST increase by 2-3 grades, 3 had gamma-glutamyl transferase (GGT) increase by 2-3 grades, and 2 had hypoglycaemia (glucose) increase by 2 grades.

Based on these findings, the Sponsor concluded that plitidepsin treatment was well tolerated and was unable to detect differences in safety between the 3 doses studied. Overall, the safety profile in the APLICOV-PC study for 1.5 to 2.5 mg Dx3 treatment was consistent with that established for cancer patients receiving their first cycle of treatment with the equivalent of 8.75 mg/day on a Days 1 and 15 Q4W schedule.

Table 1: Grade ≥ 3 Adverse Events, Regardless of Relationship, in APLICOV-PC Study

MedDRA SOC Preferred Term	Dose Cohort				Total N=45
	1.5 mg N=15	2.0 mg N=15	2.5 mg N=15		
	n (%)				
Patients with any Grade ≥ 3 AE	5 (33.3)	3 (20.0)	6 (40.0)	14 (31.1)	

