7.2.1. Adverse Events

Adverse event definitions and assignment of severity and causality are detailed in [Appendix 1](#). All adverse events (AE) and adverse reactions (ARs), based on clinical signs and symptoms and laboratory measurements, will be measured daily until Day 31 (± 3 days), except treatment-related adverse events, treatment-emergent adverse events of special interest, and SAEs that will be measured daily until resolution or stabilisation to at least Grade 1, or to an acceptable level according to the investigator and the sponsor of his/her designated representative.

Adverse events will be elicited from the patient (or, when appropriate, from a caregiver, surrogate, or the patient's legally authorised representative) by the study site staff using a non-leading question such as "How are you feeling today?" or "Have you had any health concerns since your last visit?"

The investigator and any designees are responsible for detecting, documenting, and reporting events that meet the definition of an AE or SAE and remain responsible for following up AEs that are serious, considered related to the study treatment or the study, or that caused the patient to discontinue the study treatment (see [Section 4.4.2](#)).

Clinical Signs and Symptoms: AEs, including worsening of baseline signs and symptoms of disease observed by the investigator (preferably by the same physician for a same patient) or reported by patients to study nurses will be recorded and graded according to NCI-CTCAE version 5.0, accessible via internet

(http://ctep.cancer.gov/protocolDevelopment/electronic_applications/docs/CTCAE_v5_Quick_Reference_8.5x11.pdf). All events, including those considered not related to the study drugs, must be reported in the eCRF.

The following AEs will be considered and monitored as AEs of special interest: musculoskeletal disorders, CPK increases, and rhabdomyolysis; hypersensitivity reactions, cardiac events and transaminase elevations, and hepatobiliary disorders.

Laboratory Abnormalities: Laboratory abnormalities will be recorded and graded according to NCI-CTCAE version 5.0, accessible via internet (http://ctep.cancer.gov/protocolDevelopment/electronic_applications/docs/CTCAE_v5_Quick_Reference_8.5x11.pdf). Laboratory abnormalities that are of clinical significance will be recorded in Adverse Event eCRF.

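### The protocol's rules for recording a laboratory abnormality as an AE conflict and make no exception for CPK and transaminase AESIs, so the AESI count and follow-up depend on the rule a site applies

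*Protocol*

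**What the plan says.** Section 7.2.1 of the protocol lists "AEs of special interest: musculoskeletal disorders, CPK increases, and rhabdomyolysis; hypersensitivity reactions, cardiac events and transaminase elevations, and hepatobiliary disorders". No grade or ULN multiple is attached to the two laboratory items. Section 2.2 makes the frequency of treatment-emergent AESIs a secondary safety endpoint. Section 7.2.1 also requires AESIs to be followed beyond Day 31, until they resolve or stabilise.

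Four places govern when a laboratory value becomes an adverse event:

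- Section 7.2.1: "Laboratory abnormalities that are of clinical significance will be recorded in Adverse Event eCRF".
- Appendix 1, opening text: the definition of a TEAE takes in laboratory abnormalities that appear or get worse during observation, with no test of significance.
- Appendix 1, definition of an adverse event: four alternative criteria for an abnormal test, the last being "The test result is considered to be clinically relevant by the investigator".
- Appendix 1, Reporting of Adverse Events: "Abnormal laboratory tests occurring during the study must only be recorded in the AE section of the eCRF if the disorder" meets one of three triggers. The first is that the patient has symptoms of clinical importance. The second reads "Leads to a change in study dosing (omission, delay or reduction) or discontinuation from the study, significant additional concomitant drug treatment or other therapy". The third is that one of the SAE outcomes follows. Every other result goes to the laboratory pages of the eCRF.

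Section 8.7 bases the AE analysis on reported AEs. Separately, it tabulates laboratory values by worst CTCAE grade and by shift from baseline.

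**The concern.** The reporting rule is an exclusive list. It omits the investigator-relevance criterion found earlier in the same appendix and the clinical-significance test of Section 7.2.1. It does not carve out the two AESIs that are laboratory findings by definition.

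The AESI endpoint is built from what sites enter on the AE form. If sites work from different rules, the same ALT or CPK result becomes an AESI at one site and a line on a laboratory page at another. About 103 sites are planned and the trial is open-label, so the choice is made by someone who knows the arm. The between-arm comparison of AESI frequency could then shift in either direction for reasons unrelated to the drug. The AESI follow-up duty may also start at one site and not at another.

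**Working it through.** There is no stated figure to reproduce, so the check is a comparison of the texts on one test case: a Grade 3 ALT or CPK rise on Day 8, without symptoms, untreated, not serious, and leading to no change in study dosing.

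| Rule | Does it become an AE? |
|---|---|
| Appendix 1, opening text | Yes, it is a TEAE |
| Section 7.2.1 | Yes, if judged clinically significant |
| Appendix 1, AE definition | Yes, if the investigator judges it relevant |
| Appendix 1, reporting rule | No, laboratory page only |
| Section 7.2.1, AESI list | It falls in a named AESI category, with no threshold |

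**How far the reporting rule excludes.** Two of its three triggers need no symptoms. An asymptomatic rise that changes study dosing, leads to discontinuation, needs significant treatment or has an SAE outcome is recorded. What it excludes is the remainder, as in the test case.

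**Whether the dosing trigger rescues late samples.** Plitidepsin is given on Days 1 to 3 and Section 5.2.1 allows no dose reduction, so for plitidepsin the trigger has little room to act after Day 3. The rule speaks of study dosing, however, and Section 8.4 counts dexamethasone and the control-arm antivirals as study treatment. Table 5 in Appendix 5 schedules dexamethasone to Day 10 and remdesivir or favipiravir to Day 5. The trigger can therefore still act after Day 3, but through different drugs in different arms.

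**Follow-up.** Section 7.2.1 ends AE follow-up at Day 31, except for treatment-related AEs, AESIs and SAEs. The opening text of Appendix 1 follows any TEAE, laboratory abnormalities included, to at least Grade 1 or stabilisation. A rise kept off the AE form would still be followed under the second text, but may not trigger AESI follow-up under the first. The two texts do not agree.

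**Can the effect be sized?** Section 1.2 reports that in the earlier phase 1 study of 45 patients "5 patients had ALT increase by 2-3 grades, 2 had AST increase by 2-3 grades". If the ALT rate carried over (an assumption), 5/45 = 11.1%, and 203 × 5/45 = 22.6 patients per arm would have such a shift. If a share c of these reached the AE form, 22.6 × (1 − c) would be absent from the AESI count. Nothing in the protocol fixes c, so the result runs from 0 (c = 1) to 22.6 (c = 0). That study also had no control arm, so the rate has no basis for control patients. The size cannot be derived.

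**The case against.** The strongest reply is that the safety signal is captured elsewhere. CPK, ALT and AST are measured centrally in all arms and CTCAE-graded. They form a separate laboratory endpoint in Section 2.2, reported as worst grade and shift tables that need no decision by the investigator. This stands: the values remain in the trial. But those tables neither correct the AESI frequency endpoint nor start AESI follow-up.

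A second reply is that Section 7.2.1 names these findings as AESIs, and a site may let that specific statement override the general reporting rule. Some sites may. The protocol does not say so, and Section 7.2.1 itself refers to Appendix 1 for AE definitions.

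A third is that deriving laboratory AESIs and setting a threshold belong in a statistical analysis plan. That is fair for the derivation. An analysis plan cannot, however, change what sites are told to enter or which events they must follow.

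Stronger readings are tempting and are not supported:

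- A reader might infer that most laboratory AESIs will be missed. The share captured is unknown.
- A reader might set the five ALT shifts in the earlier study against the single event of special interest reported there and call the difference a recording gap. The single event is described as a Grade 3 or higher ALT elevation, while the five are shifts of 2 to 3 grades, which can end below Grade 3. The recording rules of that study are not given.
- A reader might infer that all asymptomatic abnormalities are barred, or that the dosing trigger is dead after Day 3. The first is too broad, and the second holds only for plitidepsin.

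**Conclusion.** The concern holds as an internal conflict that bears on a stated endpoint. Under the Appendix 1 reporting rule, a CPK or transaminase rise that is asymptomatic, untreated, non-serious and without effect on study dosing stays off the AE form. Under Section 7.2.1, the Appendix 1 AE definition or the Appendix 1 TEAE definition, it may be or is an AE. AESI frequency, and whether AESI follow-up is triggered, therefore depend on the rule an open-label site applies. The direction of any bias is open and its size cannot be derived. The conclusion rests on the wording alone and assumes only that sites may follow the reporting rule as written. It should be corrected, but it does not remove the laboratory safety data from the trial.

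**What to change.** 1. Reconcile Section 7.2.1 and the three parts of Appendix 1 (opening text, AE definition, reporting rule) so that one recording rule, identical in all arms, covers the AESI laboratory analytes. Except those analytes from the exclusive list in the reporting rule.
2. Reconcile the follow-up wording in Section 7.2.1 with that in the opening text of Appendix 1.
3. In Section 8.7, add a laboratory-based AESI derived by program from the central-laboratory values already collected. Use one prespecified CTCAE criterion chosen by the sponsor, and report the result beside investigator-recorded AESIs.

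The cost is a wording change, one derivation from existing data and a few more eCRF entries. Reported AESI counts will be higher, which the report should explain.
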